### Adverse Events

AEs will be assessed throughout the study period (from pre-surgery Day -45 up to post-surgery follow-up for Month 12). For more details, refer to Section 13.1.

AEs will be deemed treatment emergent if the onset date is on or after the date of surgery. Any AEs recorded prior to the start of surgery will be listed separately from the treatment emergent AEs. Only treatment emergent adverse events (TEAEs) will be summarized. Ocular treatment emergent adverse events will be summarized separately by SOC and PT.

Both subject and event counts will be presented for AEs. Subject counts refer to the number of subjects with the respective AE of interest. Subjects who experience multiple AEs for a PT will be counted once, similarly for subjects with multiple AEs per SOC, for subject counts. Event counts refer to the number of occurrences of the respective AE of interest, regardless of whether a subject already had this event.

All information obtained on AEs (including those which are collected pre-surgery as well as TEAEs) will be displayed by treatment and subject.

Although the surgery is planned to be bilateral, the investigator may decide to not perform the surgery on the second eye on the same day as the first eye. In the following scenarios, if during the 12-month post-surgery study period:

- no surgery is performed on the second eye
- surgery is performed on the second eye using a non-study surgery

Then only AEs will be collected for the second eye.

These AEs (including those which are collected pre-surgery as well as those after the planned surgery) will be listed separately.

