6.3.1 Adverse Events

The applicable definition of an AE is in the study protocol. All AEs occurring from when a subject signs the ICF to when a subject exits the study will be accounted for in the reporting. Analysis and presentation of AEs occurring during the 45 day pre-surgery period (the screening period) will be separated from those occurring during the post-surgery period where a comparative evaluation (descriptive only) of treatment-emergent AEs (TEAEs) is intended. A TEAE is an event not present prior to surgery (Topography Guided LASIK, SMILE) or any pre-existing event that worsens following surgery. The period for TEAE analysis starts from when study treatment has begun to 12 months post-surgery (Day 330 to Day 375). Study treatment will be considered to have begun once the flap creation is initiated for Topography Guided LASIK and once the laser touches the eye for SMILE.

Descriptive summaries (subject counts and percentages, event counts) by surgery group for specific AEs will be presented by primary SOC and PT of the Medical Dictionary for Regulatory Activities (MedDRA) dictionary (Version 19.0 or a more recent version). The SOCs will be presented in alphabetical order. PTs will be ordered for each surgery group in decreasing proportion in the Topography Guided LASIK surgery group of interest (study surgery group 1). The following summary tables will be provided:

- Ocular AEs for all eyes in the Safety Analysis Set (TEAE only)
- Ocular SAEs for all eyes in the Safety Analysis Set (TEAE only)
- Adverse device effects (ADEs) for all eyes in the Safety Analysis Set (TEAE only)

- Serious ADEs (SADEs) for all eyes in the Safety Analysis Set (TEAE only)

Both subject and event counts will be presented for AEs. Subject counts refer to the number of subjects with the respective AE of interest. Subjects who experience multiple AEs for a PT will be counted once, similarly for subjects with multiple AEs per SOC, for subject counts. Event counts refer to the number of occurrences of the respective AE of interest, regardless of whether a subject already had this event.

Individual subject's listings will also be provided. These will include:

- Ocular AEs for all eyes in the Safety Analysis Set
- Ocular AEs for all eyes not in the Safety Analysis Set
- Non-ocular AEs for all enrolled subjects
- Listing of deaths for all enrolled subjects

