10.1.1.2 AE Start Date

AEs with completely missing onset dates will be considered to be treatment emergent. AEs with partially missing onset dates will also be included as treatment emergent when the month (if it exists) and the year occur on or later than the month and year of first administration of study treatment.

Partial AE start dates are imputed with reference to the first administration of study treatment (TRTSTD) as outlined in the table below.

The date value is split into day, month, and year sections and referenced in the imputation table as outlined below:

| | Day | Month | Year |
|-----------------------|----------|-------|------|
| Partial AE Start Date | Not used | MON | YYYY |

| | Day | Month | Year |
|-------------------------------------|----------|-------|------|
| Study Treatment Start Date (TRTSTD) | Not used | TRTM | TRTY |

The following matrix explains the logic behind the imputation.

| Comparison of month section | MON missing | MON<TRTM | MON=TRTM | MON>TRTM |
|-----------------------------|---|--|--|--|
| YYYY missing | NC | NC | NC | NC |
| YYYY<TRTM | (D) = 01JULYYYY Before Study Treatment Start | (C) = 15MONYYYY Before Study Treatment Start | (C) = 15MONYYYY Before Study Treatment Start | (C) = 15MONYYYY Before Study Treatment Start |
| YYYY=TRTY | (B) = TRTSTD+1 Uncertain | (C) = 15MONYYYY Before Study Treatment Start | (A) = = TRTSTD+1 Uncertain | (A) = = 01MONYYYY After Study Treatment Start |
| YYYY>TRTY | (E) = 01JANYYYY After Study Treatment Start | (A) = = 01MONYYYY After Study Treatment Start | (A) = = 01MONYYYY After Study Treatment Start | (A) = = 01MONYYYY After Study Treatment Start |

The following table is the legend to the logic matrix.

| | |
|--|--|
| Relationship | |
| Before Study Treatment start | Partial date indicates AE start date prior to Study Treatment Start Date |
| After Study Treatment start | Partial date indicates AE start date after Study Treatment Start Date |
| Uncertain | Partial date insufficient to determine relationship of AE start date to Study Treatment Start Date |
| Imputation calculation | |
| NC / Blank Uncertain | No convention |
| (A) After Treatment Start or Uncertain | MAX(01MONYYYY, TRTSTD+1) |
| (B) Uncertain | TRTSTD+1 |
| (C) Before Study Treatment Start | 15MONYYYY |
| (D) Before Study Treatment Start | 01JULYYYY |
| (E) After Study Treatment Start | 01JANYYYY |

Before imputing the AE start date, find the AE start reference date.

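### Protocol and SAP define treatment-emergent AEs differently, and the SAP's missing-onset flag has no end-date check, so it can count events that ended before surgery

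*Protocol*

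**What the plan says.** **Protocol 15.7, Adverse Events.** The rule is a calendar-date rule: "AEs will be deemed treatment emergent if the onset date is on or after the date of surgery". It has no clause on worsening. The next sentence cuts at the start of surgery instead: "Any AEs recorded prior to the start of surgery will be listed separately from the treatment emergent AEs". The section then adds: "Only treatment emergent adverse events (TEAEs) will be summarized".

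**SAP 6.3.1.** "A TEAE is an event not present prior to surgery (Topography Guided LASIK, SMILE) or any pre-existing event that worsens following surgery". The analysis period opens when study treatment has begun, meaning flap creation for LASIK and laser contact for SMILE. The four AE summary tables (ocular AEs, ocular SAEs, ADEs and serious ADEs) are all limited to treatment-emergent events.

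**SAP 10.1.1.2, the flag.** "AEs with completely missing onset dates will be considered to be treatment emergent". For partial dates, "AEs with partially missing onset dates will also be included as treatment emergent", but only "when the month (if it exists) and the year occur on or later than the month and year of first administration of study treatment". Neither sentence refers to the end date.

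**SAP 10.1.1.2, the imputation steps.** If the onset year is missing, the imputed start is NULL. Otherwise, if the end date is complete and falls before treatment, the reference date moves back from treatment start to the earlier of consent and the first visit. A final step prevents the imputed start from falling after the end date.

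**The concern.** Protocol 8.5.2 names the frequency of treatment-emergent AEs as a safety endpoint. Since only treatment-emergent events are tabulated, the definition decides which events enter every AE summary comparing the two procedures. AEs are collected from consent (Protocol 13.3) and surgery may follow by up to 45 days, so events can start, and finish, before treatment. If two rules are in force, a programmer and someone checking the tables against the protocol can reach different counts from the same records. If the missing-date flag overrides an end date that proves the event was over, the tables attribute to surgery something that preceded it.

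**Working it through.** The documents give no AE rate or missing-date rate, so there is no figure to reproduce. The check is to apply each rule to constructed events. Dates are assumed for illustration: consent and first visit 5 March 2017, surgery 20 March 2017.

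| Event | Protocol 15.7 | SAP 6.3.1 | SAP 10.1.1.2 flag | SAP imputed start |
|---|---|---|---|---|
| A. Onset 10 Mar, ended 14 Mar | not emergent | not emergent | not needed | not needed |
| B. Onset 25 Mar | emergent | emergent | not needed | not needed |
| C. Onset 10 Mar, single record, worsens after surgery | not emergent | emergent | not needed | not needed |
| D. Onset 20 Mar, before flap or laser | emergent by date; listed separately by the next sentence | not emergent | not needed | not needed |
| E. Onset completely missing, ended 14 Mar | cannot be applied as written, but onset cannot be after 14 Mar | not emergent | emergent | NULL |
| F. Day unknown, Mar 2017, ended 14 Mar | not emergent on the imputed date | not emergent | emergent | 6 Mar |
| G. Day and month unknown, 2017, ended 14 Mar | not emergent on the imputed date | not emergent | emergent | 6 Mar |

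A and B are controls, and the rules agree on them. The cases were chosen to probe the rules and say nothing about frequency.

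**Case C** isolates the worsening clause. It differs only if the worsening is kept on the original record. A new record with a post-surgery onset is emergent under both documents.

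**Case D** is an inconsistency within Protocol 15.7: the date rule includes the event, and the following sentence sets it apart.

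**Case E.** The event was present, and over, before surgery, so it fails SAP 6.3.1. The flag includes it. Because the imputed start is NULL, no imputed date is available to correct the flag.

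**Cases F and G.** The end date of 14 March precedes 20 March, so the reference date is 5 March.
- F: imputed start = later of (1 March, 5 March + 1 day) = 6 March.
- G: imputed start = 5 March + 1 day = 6 March.
- The matrix in the same section uses treatment start + 1 day = 21 March for both. That is after the end date, so the final step resets it to 14 March.

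By either route the event is dated before 20 March, yet the flag calls it emergent. The SAP gives no order of precedence.

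The partial-date conflict has a bounded reach. An onset in an earlier month or year is not flagged, and an onset in a later month cannot belong to an event that ended before surgery. What remains is an onset in the treatment month and year, or in the treatment year with the month unknown. With a window of at most 45 days, consent and surgery can readily share a month or year.

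**The case against.** **Tables will be programmed from the SAP.** Protocol Section 15 leaves technical detail to the SAP, and SAP Section 1 allows for deviations, so in practice one definition would be used. That largely stands. But the SAP does not label its worsening clause as a departure, and it was written against Protocol Version 1.0 while the current protocol is Version 2.0. Nor does this argument touch the conflicts inside the SAP.

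**Worsening may already be captured.** Protocol 13.2 requires clinically relevant untoward changes in protocol-specific parameters or questionnaires to be reported as AEs. If these are entered as new AEs, case C disappears. This stands as a limit, since the documents do not say how worsening is recorded. Dry eye is a weak example: dry eye on the SQDES is an exclusion criterion, and change in it has its own shift table.

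**Counting undated events as emergent is conservative.** That is right when timing is unknown. It does not justify overriding a known end date.

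**Stronger readings to avoid.** A reader might infer that the SAP flags all partially dated AEs; the month-and-year condition rules that out. A reader might infer that every event that ended before surgery is both dated before surgery and flagged; completely missing onsets are not dated at all. A reader might also infer that the protocol plainly counts Day 0 events before the laser and that the SAP does the opposite. The protocol's next sentence separates such events, and Section 12.1.1 discontinues subjects with a complication before laser contact, which narrows the case further.

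**Conclusion.** The inconsistencies are real on the current text. The two documents differ on worsening of a pre-existing AE (if it stays on one record). Protocol 15.7 conflicts with itself on a Day 0 event before the laser. SAP 10.1.1.2 wrongly counts an AE with a completely missing onset and an end date before surgery. For partial onsets in the treatment month or year, its flag and its imputation disagree with no stated precedence.

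The size cannot be computed, and few events are likely. Exposure is limited to the window of up to 45 days before surgery, the day of surgery, and AEs with incomplete onset dates. Safety is descriptive, so significance level and power are unaffected. The SAP tables cover only ocular AEs, ocular SAEs, ADEs and serious ADEs, and pre-surgery events are still listed, so nothing is lost from the record. The documents therefore do not support inferring that the safety comparison is materially distorted. It is still worth correcting, because the rule decides entry to every AE summary table.

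**What to change.** 1. Use one definition in SAP 6.3.1 and, at the next amendment, in Protocol 15.7: onset or worsening at or after the start of study treatment, as that start is defined in Protocol 15.2 and SAP Section 3. This also settles the Day 0 case.
2. In SAP 10.1.1.2, add to both missing-date sentences an exception for any AE with a complete end date before the date of surgery. Events with an incomplete end date stay flagged, which keeps the conservative treatment where timing really is unknown.
3. State that this exclusion takes precedence over the missing-date flag.

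The cost is a few sentences in the SAP, which Protocol Section 15 says will be finalized before database lock, and minor programming. The protocol edit needs a formal amendment under Section 5 but need not prompt one; it can wait for the next.

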### **Device Deficiencies**

Device deficiency will be evaluated at day of surgery (Day 0). For more details, refer to Section 13.1.

The number and percentage of all device deficiencies will be tabulated by treatment. A listing of all device deficiencies will also be provided.

Alcon - Business Use Only Protocol - Clinical Effective Date: 19-Mar-2017 Page 74 of 81

Document: TDOC-0052425 Version: 2.0; Most-Recent; Effective; CURRENT

Status: Effective

### **Other Safety Assessments**

Other safety evaluations include slit lamp findings IOP, surgical problems, dilated fundus findings and PRO Questionnaires (RSVP, SQDES). For details refer to Section 12.1.

The mean overall and eight subscale vision related quality scores will be derived from the RSVP questionnaire.

For SQDES, a subject is defined as having dry eye syndrome if there was occurrence of both dryness and irritation of the eyes either constantly or often (that is, severe symptoms) or a report of a previous clinical diagnosis of dry eye syndrome.

Information from the nomogram, if one is used, and surgical report will also be provided.

# 15.8 Interim Analyses

There is no formal interim analysis planned. The main analysis will occur after the 3 months post-surgery follow-up. Subjects will be followed up for an additional 9 months post-surgery (i.e. in total 12 months [Day 330 to Day 375] after surgery) for safety

## 15.9 Sample Size Justification

The sample size calculation is based on conservative estimates of the interim results from a pilot study comparing Topography Guided LASIK to SMILE (single center investigator initiated trial) (data not published).

Based on the assumed rates of 90% vs 80% of eyes with manifest refraction cylinder less than or equal to 0.5 D at 3 months for Topography Guided LASIK and SMILE, respectively, and an intracluster correlation coefficient (i.e. correlation between eyes within subject) of 0.39, a sample size of 185 subjects (treated bilaterally) per treatment group will provide 90% power to reject the hypothesis for the primary effectiveness objective (based on the two-sided 5% significance level). In total, 740 eyes from approximately 370 subjects are required for this study.

To ensure the required sample size is achieved, approximately 225 subjects (contributing 2 eyes each) will be enrolled per treatment arm. This will take into account drop-outs prior to surgery. It is expected that 400 subjects (200 subjects per treatment arm) will receive bilateral treatment. Of these subjects, it is expected that a further 7% may drop out during the 3 months post-surgery.

Effective Date: 19-Mar-2017 Page 75 of 81 Alcon - Business Use Only Protocol - Clinical

Version: 2.0; Most-Recent; Effective; CURRENT **Document:** TDOC-0052425

Status: Effective

#### 16 ADMINISTRATIVE PROCEDURES

#### 16.1 **Regulatory and Ethical Compliance**

This clinical study will be conducted in accordance with the principles of the Declaration of Helsinki, and in compliance with ISO 14155:2011 Clinical investigation of medical devices for human subjects, GCP, the Code of Federal Regulations (CFR), and laws and regulations of foreign countries, whichever affords greater protection to subjects. The study will also be conducted in accordance with the Sponsor's Standard Operating Procedures (SOPs) and all other applicable regulations. The Investigator and all clinical study staff will conduct the clinical study in compliance with this protocol. The Investigator must ensure that all personnel involved in the conduct of the clinical study are qualified to perform their assigned duties through relevant education, training, and experience.

#### 16.2 **Informed Consent Procedures**

Voluntary informed consent must be obtained from every subject prior to the initiation of any screening or other clinical study-related procedures. The Investigator must have a defined process for obtaining consent. Specifically, the Investigator, or designee, will explain the clinical study to each potential subject and the subject must indicate voluntary consent by signing and dating the approved ICF. The subject must be provided an opportunity to ask questions of the Investigator, and if required by local regulation, other qualified personnel. The Investigator must provide the subject with a copy of the consent form written in a language the subject understands. The consent document must meet all applicable local laws and will provide subjects with information regarding the purpose, procedures, requirements, and restrictions of the clinical study, along with any known risks and potential benefits associated with the investigational product, the available compensation, and the established provisions for maintaining confidentiality of personal, protected health information. Subjects will be told about the voluntary nature of participation in the clinical study and will be provided with contact information for the appropriate individuals should questions or concerns arise during the clinical study. The subject also will be told that their records may be accessed by appropriate authorities and Sponsor-designated personnel. The Investigator must keep the original, signed copy of the consent and must provide a duplicate copy to each subject.

### 16.3 Responsibilities of the Investigator and IRB/IEC

Before clinical study initiation, this protocol, the ICF (and assent form, if applicable), any other written information provided to subject, and any advertisements planned for subject recruitment must be approved by an IRB / Independent Ethics Committee (IEC). A master list

Print Date: Printed By:

Alcon - Business Use Only Protocol - Clinical Effective Date: 19-Mar-2017 Page 76 of 81

Document: TDOC-0052425 Version: 2.0; Most-Recent; Effective; CURRENT

Status: Effective

of IRBs/IECs for this clinical study can be found in the Trial Master File. The Investigator must provide documentation of IRB/IEC approval to the Sponsor. The approval must be dated and must identify the applicable protocol, amendments (if any), ICF, assent form (if any), all applicable recruiting materials, written information for subjects, and subject compensation programs. The IRB/IEC must be provided with a copy of the Directions for Use, any periodic safety updates, and all other information as required by local regulation and/or the IRB/IEC. At the end of the clinical study or in the case of early termination, the Investigator will notify the IRB/IEC of the clinical study's final status. Finally, the Investigator will report to the IRB/IEC on the progress of the clinical study at intervals stipulated by the IRB/IEC.

# **16.4** Sponsor and Monitoring Responsibilities

The Sponsor will designate a monitor to conduct the appropriate site visits at the appropriate intervals. The clinical investigation will be monitored to ensure that the rights and wellbeing of the subjects are protected; the reported data are accurate, complete, and verifiable from the source documents; the equipment used to assess variables in the clinical investigation is maintained and calibrated per manufacturer instructions and Sponsor requirements; and the study is conducted in compliance with the current approved protocol (and amendment[s], if applicable), with current GCP, and with applicable regulatory requirements. All investigative sites will have a site initiation. Monitoring will be conducted periodically while the clinical study is ongoing. Monitoring methods may include site visits, telephone, written, and fax correspondence. The assigned CSM will contact each site at appropriate intervals. The Lead Clinical Site Manager (LCSM) will determine the frequency of site visits. Close-out visits will take place after the last visit of the last subject. Enrollment will be tracked and reported at regular intervals. Details regarding enrollment (eg, number of subjects pre-screened, screened, reasons for screen failures, etc.) may be requested of the investigative site and must be provided within a reasonable time period. The Sponsor will be responsible for implementing and maintaining quality assurance and quality control systems to ensure the study is conducted and data are generated, documented and reported in compliance with the protocol, GCP and applicable regulatory requirements.

The Sponsor will secure agreement from all involved parties to ensure direct access to all study related sites, source data and documents, and reports for the purpose of monitoring and auditing by the Sponsor, and inspection by domestic and foreign regulatory authorities. Quality control will be applied to each stage of data handling to ensure that all data are reliable and have been processed correctly. Agreements made by the Sponsor with the

Effective Date: 19-Mar-2017 Page 77 of 81 Alcon - Business Use Only Protocol - Clinical

Version: 2.0; Most-Recent; Effective; CURRENT Document: TDOC-0052425

Status: Effective

Investigator/Institution and any other parties involved in the clinical study will be provided in writing as part of the protocol or as a separate agreement.

